## **STATISTICAL CONSIDERATIONS**

### **Sample size**

There are currently no effectiveness studies on the psychological interventions for CPTSD to enable power calculations. Following a pragmatic approach and in line with previous pilot studies in the area of PTSD we will aim to recruit  $n=30$  individuals per arm (total sample = 60). This approach will enable us calculating sample size for an adequately powered trial.

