#### ***Quantitative analyses***

The main analyses of the trial data will be conducted in 2 phases; (1) modelling within-subject changes in ITQ scores for data from the ESTAIR arm of the trial and a (2) comparison between the ITQ scores, and secondary outcome measures, for the ESTAIR and TAU groups at 25 weeks and 12 week follow-up.

Phase 1: An analogue to a repeated measures ANOVA will be specified as a structural equation model to handle missing data efficiently using robust maximum likelihood estimation (MLR: Schafer & Graham, 2002) and relax assumptions about the variance-covariance structure of the observations (Hoffman, 2015). An initial model will specify and estimate a model with the mean ITQ scores from the five observation periods (baseline, 7, 13, 19, 25 months) constrained to be equal, and then the model will be re-estimated with the means to be freely estimated. The difference in model fit can be tested using the loglikelihood difference test, which is distributed as a chi-square ( $\chi^2$ ). A significant  $\chi^2$  result indicates that the unconstrained model is better than the constrained model, meaning that the null hypothesis of equal means can be rejected (Hoffman, 2015). If this is the case pairwise differences in means will be tested using the Wald  $\chi^2$  test. The magnitude of the change in symptoms scores will be calculated using Cohen's  $d$  with a correction for repeated measures designs (dr). Values  $< 0.40$  reflect 'small' effects, values from 0.40 to 0.79 reflect 'medium' effects, and values  $> 0.80$  reflect 'large' effects.

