Phase 2: The primary intention to treat analysis will be conducted to examine differences between the ESTAIR and TAU groups at 25 weeks. This analysis will be conducted using a regression approach, simultaneously regressing the 25 week mean scores of the ITQ, PHQ-9, GAD-7, PHQ-15, and AUDIT onto a dummy-coded binary variable representing the treatment and control group (ESTAIR = 1, TAU = 0). The estimated regression coefficient for each variable indicates the mean difference between the treatment and control group, and the associated  $p$ -values indicate statistical significance. This approach was used as (1) all the model parameters are estimated simultaneously thereby avoiding the need for post-hoc adjustment for multiple testing, (2) the use of robust maximum likelihood (MLR) estimation allows for missing data to be handled efficiently by using all available data (Schafer & Graham, 2002), and third, MLR estimation is robust against deviations from normality and produces unbiased standard errors (West, Finch, & Curran, 1995). Furthermore, the

standardised regression coefficients from this model can be used as a useful analogue to Cohen's *d* as a measure of effect size (Nieminen, Lehtiniemi, Vähäkangas, Huusko, & Rautio, 2013): *d*=0.20 is a 'small' effect, *d*=0.50 is a 'medium' effect, and *d*=0.80 is 'large' effect size.

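### Phase 2 puts the standardised coefficient of a 0/1 arm variable on Cohen's d cut-offs without naming the standardisation or converting it; fully standardised, it is about half of d

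*Combined protocol and SAP*

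**What the plan says.** In Data analysis, Quantitative analyses, Phase 2, the 25-week scores on the ITQ, PHQ-9, GAD-7, PHQ-15 and AUDIT are regressed together on a "dummy-coded binary variable representing the treatment and control group (ESTAIR = 1, TAU = 0"). There are no covariates. The plan interprets the raw coefficient correctly: "The estimated regression coefficient for each variable indicates the mean difference between the treatment and control group". Estimation is by robust maximum likelihood, and the stated reason is that "the use of robust maximum likelihood (MLR) estimation allows for missing data to be handled efficiently by using all available data".

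It then turns to effect size. The "standardised regression coefficients from this model can be used as a useful analogue to Cohen's" *d*, and the benchmarks follow directly: "0.20 is a 'small' effect", "0.50 is a 'medium' effect", and 0.80 is large. A methods paper is cited for the analogy. The text does not say which variables are standardised, which SD is used, or how a coefficient is turned into d, and no other section supplies this.

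Phase 1 takes a different route for change within the ESTAIR arm. It names Cohen's d "with a correction for repeated measures designs (dr"), though without a formula.

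**The concern.** The term standardised coefficient can mean two things here. In ordinary usage both predictor and outcome are scaled to unit SD. For a single binary predictor that makes the coefficient a point-biserial correlation, which cannot exceed 1 in absolute value and is not on the d scale. If only the outcome is scaled, the coefficient is the mean difference in units of the total outcome SD, which is close to d. Both readings fit the sentence in the plan, and they differ about twofold.

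This is the only standardised between-arm effect size in the plan, and it applies to all five outcomes of the primary intention-to-treat comparison. On the first reading, ESTAIR versus TAU would be reported at roughly half its size on the d scale, and many effects would get too low a verbal label. If the choice is made only at the analysis stage, the label depends on a software option and could be picked with the data in view.

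**Working it through.** **Inputs.**
- Arm coded 0/1, no covariates (Phase 2).
- Cut-offs 0.20, 0.50 and 0.80 (Phase 2). These are conventions, so there is no plan figure to reproduce.
- Thirty "individuals per arm (total sample = 60") (Sample size), so the ESTAIR share is p = 0.5.
- Assumed: equal within-arm SD. The simulation also assumes normal outcomes and complete data.

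**Formulas.** With within-arm SD 1 and mean difference d, the total outcome variance is 1 + p(1−p)d² and the SD of the arm variable is √(p(1−p)).
- Both standardised: β = d√(p(1−p)) / √(1 + p(1−p)d²). At p = 0.5 this is d/√(d² + 4).
- Outcome only: β = d / √(1 + p(1−p)d²). At p = 0.5 this is d/√(1 + d²/4).

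For d = 0.50: 0.50/√4.25 = 0.2425 and 0.50/√1.0625 = 0.4851.

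| True d | Both standardised (ratio to d) | Outcome only (shortfall) |
|---|---|---|
| 0.20 | 0.0995 (0.498) | 0.1990 (0.5%) |
| 0.50 | 0.2425 (0.485) | 0.4851 (3.0%) |
| 0.80 | 0.3714 (0.464) | 0.7428 (7.2%) |

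**True d needed to reach each cut-off.** Inverting the first formula at p = 0.5 gives d = 2β/√(1−β²).
- Both standardised: β of 0.20, 0.50 and 0.80 needs d of 0.408, 1.155 and 2.667.
- Outcome only: 0.201, 0.516 and 0.873.

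**Which labels change (both standardised).** The plan does not say how values between the benchmarks are labelled, so both usual readings were tried.
- Cut-offs as lower bounds: the label is too low for d from 0.20 to 0.41 and from 0.50 to 2.67. It is unchanged below 0.20, from 0.41 to 0.50, and above 2.67.
- Nearest benchmark (switching at 0.35 and 0.65): the label is too low for d from 0.35 to 1.71 and unchanged outside that range.

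**Simulation.** 40,000 trials per value of d, 30 per arm, labels on absolute values. The table gives the share of trials in which the coefficient's label is lower than the label from pooled-SD d (lower-bound reading / nearest reading).

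| True d | Both standardised | Outcome only |
|---|---|---|
| 0.2 | 46% / about 30% | 1% / 1% |
| 0.5 | 73% / 72% | 5% / 3% |
| 0.8 | 93% / 96% | 9% / 3% |

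**Confidence interval.** By noncentral t, an observed d of 0.50 with 30 per arm has a 95% interval of −0.016 to 1.012. On the fully standardised scale the same interval is −0.008 to 0.452. So data compatible with a large effect would show an interval that stops short of the medium cut-off. With 45 of 60 analysed (the 75% in Progression Criteria for a Full Trial, taken as 22 and 23 per arm), the intervals are −0.097 to 1.091 and −0.048 to 0.479.

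**Unequal arms.** With an assumed p = 0.40 (18 of 45), full standardisation gives 0.0975, 0.2379 and 0.3649. Converting these back as if the arms were equal gives d = 0.196, 0.490 and 0.784. Using p in the conversion returns 0.20, 0.50 and 0.80.

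**The case against.** The strongest counter-argument is that the harm depends on a reading that the plan does not state. The text has just described the raw coefficient as a mean difference, and a mean difference over the outcome SD would be a fair analogue of d. On that reading the cut-offs nearly fit. This stands as a limit on the claim: the documents do not show that mislabelling will happen. It does not close the gap, because full standardisation is the ordinary meaning of the term and nothing in the plan excludes it.

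The cited methods paper may contain the rule. It cannot be read here, so nothing is claimed about its content. The plan itself states neither the version nor a conversion.

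The wording is permissive: the coefficient can be used, and only as an analogue. But the d benchmarks follow at once, and an analogue on another scale cannot be read against them.

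Phase 1 is not fully specified either, since it gives no formula for its correction. That is fair, and the contrast should not be pressed beyond noting that Phase 1 names d itself.

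Finally, this is a pilot whose research questions concern recruitment, retention and acceptability, and with intervals about one d unit wide no verbal label is secure. That limits the consequences and is a reason to report an interval. It is no reason to leave the scale undefined.

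**Conclusion.** The concern holds, as a conditional one. The plan places a standardised coefficient on d cut-offs without defining it. If arm and outcome are both standardised, the reported value is 0.46 to 0.50 of d for d between 0.2 and 0.8, an effect of 0.5 is called small, and an effect of 0.8 is not called large. If only the outcome is standardised, the understatement is 0.5% to 7% and labels rarely change. The figures rest on equal arms and equal within-arm SDs; the label shares also assume normality and complete data.

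Raw mean differences, p-values and the progression criteria are untouched. The plan does not say that this coefficient will feed the sample size of a full trial, so no harm is claimed there. It should be fixed before results are reported. Confidence is medium, because the intended standardisation is unknown.

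**What to change.** Define the Phase 2 effect size as the unstandardised arm coefficient divided by the pooled within-arm SD at 25 weeks (divisor n − 2), with a 95% confidence interval, and apply the 0.20, 0.50 and 0.80 cut-offs to that.

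Two details for the analyst:
- If the SD comes from the maximum-likelihood residual variance (divisor n), multiply that SD by √(n/(n−2)), where n is the number of participants with that outcome. Without this, d is inflated by a factor of √(60/58) = 1.017 at n = 60 or √(45/43) = 1.023 at n = 45. The correction is minor, and approximate when outcomes are incomplete.
- If the fully standardised coefficient is also reported, name it as such and convert it with d = β/√(p(1−p)(1−β²)), where p is the ESTAIR share used to standardise the arm variable in the fitted model. Then multiply by √((n−2)/n) to match the pooled-SD version. With complete data this returns pooled-SD d exactly.

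The cost is two or three sentences in the analysis plan and one or two lines of code. No extra data are needed and the model does not change.

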### ***Qualitative analyses***

Qualitative data regarding acceptability of the intervention and the outcomes will be recorded and summarised. Qualitative data will be analysed using the thematic analysis guidelines (Braun & Clarke, 2006).

## **OPERATIONAL CONSIDERATIONS**

### **Risks associated with research**

#### ***Assessment and management of increased distress***

Some of the non-clinical research procedures (interviews and questionnaires) involve divulging personal and sensitive information in relation to current symptoms and mood, including suicidal ideation. In relation to symptoms, the questionnaires and measures to be used in this study (ITQ, GAD, PHQ) are routinely used in healthcare practice, without reported adverse effects.

Prior to study commencement, the research assistant will be fully trained on how to respond to any increased distress. During the study, they will receive weekly supervision by experienced clinical psychologists, who will also be directly contactable by phone during the research interviews. If the participant experiences mild distress, the RA will stay with them until any distress subsides. They will listen empathically and will help them to arrange contact with their clinician. If their distress is more severe the RA will immediately contact their supervisor for instruction. As far as possible, participant appointments for assessments will be scheduled alongside their clinical appointments so clinicians are available. All participants will be provided with contact details for relevant support organisations in the unlikely event that they feel distressed after leaving the appointment. They will also have the contact details of the RA should they have any further questions following the study. Participants will be regularly reminded that they are free to withdraw from the study at any point, without providing a reason and that their usual treatment will remain unaffected. Therapy sessions will be provided by an experienced therapist and any distress that might arise during therapy will be dealt with as per normal clinical practice.

#### ***Management of disclosures (harm to self or others)***

The study involves questions about traumatic stress, which is associated with self-harm. As people will have regular contact with a clinician for their treatment, an imminent risk of harm to self or others will already be known and managed appropriately. However, in some cases the clinical team may not be aware of this risk. In all cases, participants will be informed that their data will be held confidentially but if they disclose information which suggests an imminent risk of harm to them or someone else, then the research team are obliged take steps to reduce this risk, which in most cases will involve them sharing their concerns immediately with their GP who will then take over the clinical management. The research assistant will act at all times under supervision of an experienced clinical psychologist in assessing and managing this process, ensuring both they and the participant are fully supported and safe.

### ***Burden of non-clinical (research) procedures***

For ethical and pragmatic reasons, we have designed the assessments to involve as less burden as possible. We have minimised the number of assessment points and have carefully selected our measures to avoid duplication and gather only essential information.

The initial consent process and assessment of research capacity will take approximately 30 minutes. The initial baseline assessment (week 0) will take approx. 60mins to complete. Self-rated assessments will be used.

### ***Researchers and clinicians***

Meetings with participants will be conducted at Combat Stress venues or on-line through a secure platform. If therapy is conducted face to face, the research assistant and clinician will be aware of the safety measures available in treatment rooms (i.e. alarm buttons). The supervision team will be contactable throughout in the case that support or advice is required. In addition, clinical oversight for the project will be provided by [name] (Psychiatrist and Director at Combat Stress).

There is a small risk of researchers or clinicians being involved in an accident while travelling for the purposes of research. We will encourage all researchers who are required to travel as part of this project to use safe forms of transport (own vehicle or public transport) and to plan their journeys carefully to ensure their and others' safety. Outward travelling for research purposes will not be allowed before 7am or after 4pm. We will require all researchers to allow sufficient time for travelling to and from meetings, to avoid accidents as a consequence of haste.

### ***Vicarious trauma***

There is a small risk of research staff or clinicians experiencing vicarious trauma, whereby listening to participants describe their own traumatic events has a secondary emotional effect on them. All research and clinical staff will receive regular supervision and support from experienced clinical psychologists (the Chief Investigators). A standing item on the supervision agenda will be self-care, and supervisors will monitor – and encourage staff to self-monitor - for any signs of distress. By careful management of the flow of participants, we will ensure the research and clinical caseloads of all staff are shared equally, and we will suspend recruitment if there is any sign of the research or clinical staff feeling stressed or anxious because of demands. We will also encourage the research team to provide each other with social support, and researchers will be encouraged to seek help from their GP or occupational health should mental health problems emerge (whether related to the study or not).

## **Ethical considerations and good clinical practice**

### ***Ethical Conduct***

This study will be conducted in accordance with the principles of the International Conference on Harmonisation Tripartite Guideline for Good Clinical Practice (ICH GCP). Before the study commences, all required approvals will be obtained and any conditions of approvals will be met.

### ***Investigator Responsibilities***

The Investigator is responsible for the overall conduct of the study at the site and compliance with the protocol and any protocol amendments. In accordance with the principles of ICH GCP, the following areas listed in this section are also the responsibility of the Investigator. Responsibilities may be delegated to an appropriate member of study site staff. Delegated

tasks will be documented on a Delegation Log and signed by all those named on the list prior to undertaking applicable study-related procedures.

### *Informed Consent*

For potential participants entering the study, the research assistant will discuss the study with them, answer any questions, give them an information sheet, and seek their consent to pass on their details to the research team.

### *Data Recording*

All research and clinical staff will receive full training data quality, secure data management, maintaining confidentiality and record-keeping.

### *Good Clinical Practice (GCP) Training*

Although GCP training is not a mandatory requirement for non-CTIMP studies such as this one, all research staff with contact with participants or patient identifiable data will be encouraged to complete this before handling data, recruitment of participants or assessments.

### *Confidentiality*

Anonymized patient outcome data from the study will be stored on Combat Stress and University computers for data analysis. These computers are password protected. All hard copies of completed questionnaires used in the study will be made anonymous using a coding system and any personal identifiable information will be removed. These will be scanned and stored in an encrypted format on a secure University password-protected computer system. Participant consent forms will contain names, contact details and identification code of the participant so that relevant questionnaire scores can be matched to the same participant. These will be scanned and stored in an encrypted format in a separate file on a secure Combat Stress password-protected computer system and will not be removed from Combat Stress premises.

Clinical procedures (therapy sessions), non-clinical procedures (research assessments and qualitative interviews) will be audio-recorded with participant consent, using encrypted and password secured audio recording devices. This is to enable (a) checks on therapy fidelity by the clinical supervisor (b) accurate ratings of interview responses by the research assistant and their supervisor and (c) transcription and analysis of qualitative interviews. Any personally identifiable data, including recordings and consent forms, will not leave Combat Stress premises and will be stored in line with the procedures above. Anonymized data (i.e., database of questionnaire scores, linked to anonymous participant ID, will be held in secure password-protected storage on Combat Stress or University computers. Anonymized and password-protected data may be shared by email within the Research Team, for the purpose of statistical analysis.

Only the informed consent forms and audio recordings will contain any participant identifiable data. Completion of the consent form will link the participant to a unique identification code which will be attached to all subsequent data (questionnaires and recordings). Data is not anonymous as such but will not be traceable to any particular individual unless access to the consent form is obtained. The list of codes and consent forms will be kept separately from one another in a different encrypted and password protected file on a secure Combat Stress computer system. Only the lead researchers and researchers with direct participant contact will have access to the file. All data will be held securely and treated in accordance with the BPS (2009) Code of Ethics and Conduct and BPS (2014) Code of Human Research Ethics guidelines documents and the study will adhere to the principles of Good Clinical Practice.

## **STUDY CONDUCT RESPONSIBILITIES**

### **Protocol Amendments**

Any changes in research activity, which involve a change in the study protocol (except those required to manage an urgent safety issue), will be reviewed and approved by the Chief Investigator. All study amendments will be submitted to a Sponsor representative for review and authorization.

### **Serious Breach of Protocol Requirements**

A serious breach is a breach which is likely to effect to a significant degree:

- (a) the safety or physical or mental wellbeing of the participants in the study; or
- (b) the scientific value of the study.

If a potential serious breach is identified by the Chief investigator or delegates, the Sponsor will be notified within 24 hours. The Sponsor will assess the impact of the breach on the scientific value of the study, to determine whether the incident constitutes a serious breach and report to the ethics committee as necessary.

### **Study Record Retention**

All patient identifiable information (audio files, consent forms, participant details) will be kept for a minimum of 6 months from the protocol defined end of study point, and a maximum of 12 months. All other study documentation will be stored for 10 years, in order to substantiate the research finding, and in adherence to Edinburgh Napier University policy.

### **End of Study**

The end of study is defined as the last participant's last research meeting with a participant. The Investigators or the co-sponsor(s) retain the right at any time to terminate the study for clinical or administrative reasons.

### **Continuation of Treatment/Care Following the End of Study**

The psychological intervention being tested is designed as a stand-alone discrete intervention and is considered to be complete after 25 sessions. Some of the strategies that participants being taught in ESTAIR can be used as an ongoing source of support. Following the end of the study, participants in both groups will receive appropriate support from Combat Stress as required.

